8.1.3 Uroflowmetry Parameters

The following analyses will be performed for the maximum flow rate (free Q_{\max}), average flow rate (free Q_{ave}), voided volume, and voiding time.

- 1) Summary statistics and 95% confidence intervals for the measured values at each evaluation time point (Weeks 0, 4, 8, and 12), and for the changes and percentage changes at Weeks 0, 4, 8, and 12 of the treatment period relative to baseline (Week 0), will be calculated.
- 2) Paired t-test for the measured values at baseline (Week 0) and Week 12 of the treatment period will be performed.
- 3) For the measured values at each evaluation time point (Weeks 0, 4, 8, and 12) and the changes and percentage changes from baseline (Week 0) to Weeks 4, 8, and 12 of the treatment period, the 95% confidence interval for the difference between the placebo group and the TAC-302 group will be calculated.
- 4) For the changes and percentage changes from baseline (Week 0) to each evaluation time point (Weeks 4, 8, and 12), student's t test will be performed using the placebo group as the control.
- 5) The same analyses as 1) to 4) will be performed for the case where missing data at Week 12 of the treatment period are imputed with the last observation carried forward (LOCF).

8.1.4 Post Void Residual Measured by Ultrasonography

The following analyses will be performed for post void residual measured by ultrasonography.

- 1) Summary statistics and 95% confidence intervals for the measured values at each evaluation time point (Weeks 0, 4, 8, and 12), and for the changes and percentage changes at Weeks 0, 4, 8, and 12 of the treatment period relative to baseline (Week 0), will be calculated.
- 2) Paired t-tests for the measured values at baseline (Week 0) and Weeks 4, 8, and 12 of the treatment period will be performed.
- 3) For the measured values at each evaluation time point (Weeks 0, 4, 8, and 12) and the changes and percentage changes from baseline (Week 0) to Weeks 4, 8, and 12 of the treatment period, the 95% confidence interval for the difference between the placebo group and the TAC-302 group will be calculated.
- 4) For the changes and percentage changes from baseline (Week 0) to each evaluation time point (Weeks 4, 8, and 12), student's t test will be performed using the placebo group as the control.
- 5) The same analyses as 1) to 4) will be performed for the case where missing data at Week 12 of the treatment period are imputed with LOCF.
- 6) The change and percentage change from baseline (Week 0) will be analyzed by MMRM using treatment group, evaluation time point (Weeks 4, 8, and 12 of the treatment period), and interaction between treatment group and evaluation time point as fixed effects and baseline value, sex, and age (< 65 years or \geq 65 years) as covariates. The least squares means in each treatment group, and the difference in the least squares mean between the placebo group and the TAC-302 group and its two-sided 95% confidence interval at each evaluation time point will be estimated. Unstructured covariance structure will be assumed, and toeplitz type will be used if convergence is not achieved. If convergence is still not achieved, the first-order autoregressive, compound symmetry, and variance component will be used in this order. The Kenward-Roger method (2009)⁴⁾ will be used to calculate degrees of freedom.

8.1.5 BVE [Voided Volume / (Voided Volume + Post Void Residual)]

The following analyses will be performed for BVE calculated from the voided volume measured by uroflowmetry and the post void residual measured by ultrasonography.

- 1) Summary statistics and 95% confidence intervals for the measured values at each evaluation time point (Weeks 0, 4, 8, and 12), and for the changes and percentage changes at Weeks 0, 4, 8, and 12 of the treatment period relative to baseline (Week 0), will be calculated.
- 2) Paired t-tests for the measured values at baseline (Week 0) and Weeks 4, 8, and 12 of the treatment period will be performed.
- 3) For the measured values at each evaluation time point (Weeks 0, 4, 8, and 12) and the changes and percentage changes from baseline (Week 0) to Weeks 4, 8, and 12 of the treatment period, the 95% confidence interval for the difference between the placebo group and the TAC-302 group will be calculated.
- 4) For the changes and percentage changes from baseline (Week 0) to each evaluation time point (Weeks 4, 8, and 12), student's t test will be performed using the placebo group as the control.
- 5) The same analyses as 1) to 4) will be performed for the case where missing data at Week 12 of the treatment period are imputed with LOCF.
- 6) The change and percentage change from baseline (Week 0) will be analyzed by MMRM using treatment group, evaluation time point (Weeks 4, 8, and 12 of the treatment period), and interaction between treatment group and evaluation time point as fixed effects and baseline value, sex, and age (< 65 years or ≥ 65 years) as covariates. The least squares means in each treatment group, and the difference in the least squares mean between the placebo group and the TAC-302 group and its two-sided 95% confidence interval at each evaluation time point will be estimated. Unstructured covariance structure will be assumed, and toeplitz type will be used if convergence is not achieved. If convergence is still not achieved, the first-order autoregressive, compound symmetry, and variance component will be used in this order. The Kenward-Roger method (2009) will be used to calculate degrees of freedom.

8.1.6 IPSS Score

The following analyses will be performed for the IPSS total score, IPSS storage symptoms score, IPSS voiding symptoms score, IPSS QOL score, Q1, Q3, Q5, and Q6.

- 1) Summary statistics and 95% confidence intervals for the measured values at each evaluation time point (Weeks 0, 4, 8, and 12), and for the changes and percentage changes at Weeks 0, 4, 8, and 12 of the treatment period relative to baseline (Week 0), will be calculated.
- 2) Paired t-tests for the measured values at baseline (Week 0) and Weeks 4, 8, and 12 of the treatment period will be performed.
- 3) For the measured values at each evaluation time point (Weeks 0, 4, 8, and 12) and the changes and percentage changes from baseline (Week 0) to Weeks 4, 8, and 12 of the treatment period, the 95% confidence interval for the difference between the placebo group and the TAC-302 group will be calculated.
- 4) For the changes and percentage changes from baseline (Week 0) to each evaluation time point (Weeks 4, 8, and 12), student's t test will be performed using the placebo group as the control.
- 5) The same analyses as 1) to 4) will be performed for the case where missing data at Week 12 of the treatment period are imputed with LOCF.
- 6) The change and percentage change from baseline (Week 0) will be analyzed by MMRM using treatment group, evaluation time point (Weeks 4, 8, and 12 of the treatment period), and interaction between treatment group and evaluation time point as fixed effects and baseline value, sex, and age (< 65 years or ≥ 65 years) as covariates. The least squares means in each treatment group, and the difference in the least squares mean between the placebo group and the TAC-302 group and its two-sided 95% confidence interval at each evaluation time point will be estimated. Unstructured covariance structure will be assumed, and toeplitz type will be used if convergence is not achieved. If convergence is still not achieved, the first-order autoregressive, compound symmetry, and variance component will be used in this order. The Kenward-Roger method (2009) will be used to calculate degrees of freedom.

least squares mean between the placebo group and the TAC-302 group and its two-sided 95% confidence interval at each evaluation time point will be estimated. Unstructured covariance structure will be assumed, and toeplitz type will be used if convergence is not achieved. If convergence is still not achieved, the first-order autoregressive, compound symmetry, and variance component will be used in this order. The Kenward-Roger method (2009) will be used to calculate degrees of freedom.

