3. STUDY DESIGN

This study is a central-registration, multi-center, double-blind, placebo-controlled, randomized parallel-group comparative study to investigate the efficacy and safety of TAC-302 in DU patients with OAB. The design of this study is shown in [Figure 3-1](#). This study is composed of a single-blind observation period, a double-blind treatment period, and a follow-up period.

Patients considered eligible for the enrollment in the observation period after providing written informed consent will proceed to the observation period. The investigational drug for the observation period will be administered under single-blind conditions. In the observation period, the investigational drug (placebo) will be administered orally twice daily after breakfast and dinner for 2 to 4 weeks. Patients considered eligible for the enrollment in the treatment period after the end of the observation period will proceed to the treatment period. The investigational drug for the treatment period will be administered under double-blind conditions. The investigational drug in the treatment period will be randomly assigned, with patients allocated to the TAC-302 and placebo group in a 2:1 ratio. To maintain a balance between groups, dynamic assignment using assignment factors [sex (male and female), age at informed consent (< 65 years and \geq 65 years)] will be performed. In the treatment period, the investigational drug (TAC-302 200 mg or placebo) will be administered orally twice daily after breakfast and dinner for 12 weeks. After the start of the treatment period (registration in the treatment period), patients will make visits in weeks 2, 4, 8, and 12, and the designated observations and tests will be performed. A follow-up examination will be performed 1 week after the end of week 12 of the treatment period. If any adverse event is considered to be an adverse reaction after the follow-up examination, the follow-up investigation should be performed until it is confirmed that the symptom (including abnormal laboratory values) has recovered to the state of before the onset as much as possible or is resolving.

[figure not shown]

Figure 3-1 Study Design

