2.2 Target Sample Size

2.2.1 Target Sample Size

75 patients to be enrolled in the treatment period (48 males and 27 females)

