8.1.11 Analysis by Allocation Factor

- Analyses of secondary endpoints excluding analysis of covariance/analysis using an MMRM and scatter plots (8.1.1 to 8.1.9) will be performed by age group (< 65 years and \geq 65 years).
- Analysis will be performed as for analysis of secondary endpoints by sex (8.1.1 to 8.1.9). In analysis of covariance and analysis using an MMRM, values at baseline and age (< 60 years and \geq 60 years in males and < 70 years and \geq 70 years in females) will be used as covariates.

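### The secondary-endpoint MMRMs fit one baseline slope to Weeks 4, 8 and 12, which costs some Week 12 precision if the correlation with baseline fades

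*SAP*

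**What the plan says.** SAP 8.1.4, 8.1.5, 8.1.6 and 8.1.7 (item 6 in each) and 8.1.9 (item 7) specify the same model for change and for percentage change. Besides main effects of treatment and visit, the model takes the "interaction between treatment group and evaluation time point as fixed effects and baseline value, sex, and age" category (split at 65 years) as covariates. Treatment by visit is the only interaction listed. For the residuals, "Unstructured covariance structure will be assumed, and toeplitz type will be used if convergence is not achieved", with further fallbacks and Kenward-Roger degrees of freedom. The output is the least squares mean difference from placebo, whose "two-sided 95% confidence interval at each evaluation time point will be estimated".

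The by-sex runs in SAP 8.1.11 use the same kind of model: "In analysis of covariance and analysis using an MMRM, values at baseline and age" group are the covariates, again without an interaction with visit.

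BCI and PIP1 are measured only at Weeks 0 and 12 and are analysed by ANCOVA (SAP 7.3), so Week 12 has its own baseline slope there. The pressure flow parameters in 8.1.1 and 8.1.2 are handled the same way.

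**The concern.** The model is flexible in two respects (treatment effect and covariance by visit) and rigid in a third (the baseline slope). A single slope is right only if the regression on baseline is the same at Weeks 4, 8 and 12. If the correlation weakens with time, the pooled slope leans toward Week 4, where the residual variance is smallest, and fits Week 12 worst. Week 12 is the end-of-treatment comparison.

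This matters because, for post void residual, BVE, IPSS and OABSS, the MMRM is the only comparison with placebo that adjusts for baseline; the other between-group analyses are unadjusted intervals and t-tests, with LOCF repeats. For the diary data the van Elteren test stratifies by the allocation factors, but only the MMRM adjusts for the baseline value. Baseline values are not allocation factors (Protocol 3.2.1), so chance imbalance is left to the model. These analyses serve the secondary objective of efficacy compared with placebo (SAP 1.2).

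**Working it through.** **Inputs from the documents.** 75 patients, 48 male and 27 female (SAP 2.2.1), "with patients allocated to the TAC-302 and placebo group in a 2:1 ratio" (Protocol 3), so 50:25 overall, 32:16 in men and 18:9 in women. The sample-size rationale is redacted, and no SD or correlation is given for these endpoints, so there is no plan figure to reproduce.

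**Assumed.** SD 1 at every visit, complete data, a range of correlations c with baseline at Weeks 4/8/12, and correlations between post-baseline visits that depend on their spacing in the same way.

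**Formula.** Let S be the covariance of the three visits given baseline. With unstructured covariance, the common slope (on the scale of the measured value) converges to

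b = (1′S⁻¹c) / (1′S⁻¹1).

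On the modelled scale, change from baseline, the slopes are b − 1 (applied) and c₁₂ − 1 (correct at Week 12). The Week 12 difference then carries an extra error (c₁₂ − b) × D, where D is the chance baseline imbalance, with variance 1/50 + 1/25 = 0.06 (SD 0.245). The residual part has variance 0.06 × (1 − c₁₂²). The 0.06 cancels, so

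variance ratio, one slope to visit-specific slopes = 1 + (c₁₂ − b)² / (1 − c₁₂²).

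**Worked case, AR(1) with 0.8.** c = (0.8, 0.64, 0.512). The visit weights are 0.778, 0.037 and 0.185, so b = 0.741. On the change scale the model applies −0.259 where −0.488 is right: too shallow. Ratio = 1 + (0.512 − 0.741)² / 0.738 = 1.071. The interval widens by √1.071 − 1 = 3.5%.

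| Correlations at Weeks 4/8/12 | Slope applied | Week 12 slope | Variance ratio | CI wider by |
|---|---|---|---|---|
| 0.6/0.6/0.6 (no fading) | −0.400 | −0.400 | 1.000 | 0% |
| 0.6/0.55/0.5 | −0.444 | −0.500 | 1.004 | 0.2% |
| 0.7/0.65/0.6 | −0.341 | −0.400 | 1.006 | 0.3% |
| 0.7/0.6/0.5 | −0.368 | −0.500 | 1.023 | 1.1% |
| AR(1) 0.7 | −0.407 | −0.657 | 1.071 | 3.5% |
| AR(1) 0.8 | −0.259 | −0.488 | 1.071 | 3.5% |
| 0.8/0.65/0.5 | −0.254 | −0.500 | 1.081 | 4.0% |
| 0.8/0.6/0.4 (steep) | −0.250 | −0.600 | 1.146 | 7.0% |

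Other correlations between the post-baseline visits move the middle rows by about one percentage point.

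**Simulation at 50:25** (800 trials per setting, unstructured covariance, complete data). Empirical ratios were 0.999 without fading, 0.996 for 0.6/0.55/0.5, 1.014 for 0.7/0.6/0.5, 1.087 for AR(1) 0.8 and 1.102 for 0.8/0.6/0.4. The one-slope estimate was centred on the true value, and null rejection was 5.2 to 5.6%.

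**Simulation at 18:9**, the size of the female subgroup (3,000 trials per setting). Ratios were 0.99 without fading, 0.97 for 0.7/0.65/0.6, 1.00 for 0.7/0.6/0.5 and 1.06 under AR(1)-type decay. Repeating the runs moved single values by up to about two points, so the mild settings show no dependable gain and possibly a loss of a point or two.

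**The case against.** The strongest reply is that this is an optional refinement. Nothing in the documents shows that the correlation fades. Patients must have had symptoms for at least 12 weeks and complete a 2 to 4 week placebo run-in, which fits a stable condition with mild fading at least as well as AR(1) decay. In the mild cases the loss is 3% or less. The endpoints are secondary, no power or success criterion is stated for them, and multiplicity control is declared not applicable. All of this stands, and it limits the point to a low-cost improvement.

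The further reply that model details may sit in the report analysis plan (SAP 12), or in the separately provided covariate details (SAP 11.1), carries less weight. The SAP writes out the model terms and lists no such interaction.

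Two stronger readings should be resisted. A reader might infer that the Week 12 estimate is biased or its test invalid. With complete data neither holds: randomisation balances baseline in expectation, and the covariance estimate absorbs the lack of fit into a wider but valid interval. A reader might also infer that 2:1 allocation makes the proportional loss worse. The allocation term cancels from the ratio, so it does not.

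**Conclusion.** The point holds as a conditional loss of efficiency at Week 12 in the overall-population MMRMs. It is about 0 to 3% of variance for mild fading and 7 to 8% for AR(1)-type or similar decay, reaching about 15% only if fading is steep. A ratio of 1.071 is equivalent to analysing 75 / 1.071 = 70 patients; for an effect with 80% power under visit-specific slopes, power would be 77.3%. That is a yardstick only, since the plan states no power for these endpoints.

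Every size rests on assumed correlations, complete data, unstructured covariance and the change scale. Percentage change and the fallback covariance structures were not examined.

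Incomplete data might suggest a validity problem. In a deliberately adverse simulation, with dropout tied to baseline in opposite directions in the two arms and roughly 15% missing at Week 12, the one-slope estimate was off by 0.05 to 0.08 SD and the visit-specific model was close to unbiased. Nothing in the documents indicates such dropout, so this adds a reason for the change but is not a finding against the plan. The primary-endpoint analysis is unaffected.

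**What to change.** In SAP 8.1.4 to 8.1.7 (item 6) and 8.1.9 (item 7), add the baseline value-by-evaluation time point interaction to the fixed effects, so that each visit has its own baseline slope. This replaces one slope by three, a cost of two parameters, with essentially no loss of precision at 50:25 if there is no fading.

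Do not require the term in the by-sex MMRMs of 8.1.11. With 27 women, about 18:9, it brings no dependable gain and may lose 1 to 2% unless fading is strong.

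Record the change and its reason as SAP 10 provides. If it comes after unblinding, label it as newly planned. Check that the report analysis plan carries the same model statement.

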8.1.7 OABSS Score

The following analyses will be performed for the OABSS score.

- 1) Summary statistics and 95% confidence intervals for the measured values at each evaluation time point (Weeks 0, 4, 8, and 12), and for the changes and percentage changes at Weeks 0, 4, 8, and 12 of the treatment period relative to baseline (Week 0), will be calculated. The same analysis will be performed by presence or absence of CIC.
- 2) Paired t-tests for the measured values at baseline (Week 0) and Weeks 4, 8, and 12 of the treatment period will be performed.
- 3) For the measured values at each evaluation time point (Weeks 0, 4, 8, and 12) and the changes and percentage changes from baseline (Week 0) to Weeks 4, 8, and 12 of the treatment period, the 95% confidence interval for the difference between the placebo group and the TAC-302 group will be calculated. The same analysis will be performed by presence or absence of CIC.
- 4) For the changes and percentage changes from baseline (Week 0) to each evaluation time point (Weeks 4, 8, and 12), student's t test will be performed using the placebo group as the control.
- 5) The same analyses as 1) to 4) will be performed for the case where missing data at Week 12 of the treatment period are imputed with LOCF.
- 6) The change and percentage change from baseline (Week 0) will be analyzed by MMRM using treatment group, evaluation time point (Weeks 4, 8, and 12 of the treatment period), and interaction between treatment group and evaluation time point as fixed effects and baseline value, sex, and age (< 65 years or \geq 65 years) as covariates. The least squares means in each treatment group, and the difference in the least squares mean between the placebo group and the TAC-302 group and its two-sided 95% confidence interval at each evaluation time point will be estimated. Unstructured covariance structure will be assumed, and toeplitz type will be used if convergence is not achieved. If convergence is still not achieved, the first-order autoregressive, compound symmetry, and variance component will be used in this order. The Kenward-Roger method (2009) will be used to calculate degrees of freedom.

8.1.8 KHQ Score (by Domain)

The following analyses will be performed for the score of each domain based on the Japanese version of KHQ.

- 1) Summary statistics and 95% confidence intervals for the measured values at each evaluation time point (Weeks 0 and 12), and for the change and percentage change at Week 12 of the treatment period relative to baseline (Week 0), will be calculated.
- 2) Paired t-test for the measured values at baseline (Week 0) and Week 12 of the treatment period will be performed.
- 3) For the measured values at each evaluation time point (Weeks 0 and 12) and the change and percentage change from baseline (Week 0) to Week 12 of the treatment period, the 95% confidence interval for the difference between the placebo group and the TAC-302 group will be calculated.
- 4) For the change and percentage change from baseline (Week 0) to Week 12, student's t-test will be performed using the placebo group as the control.

8.1.9 Bladder Diary Records

The following analyses will be performed for the average number of micturitions per 24 hours, average number of urgency urinary incontinence episodes per 24 hours, average number of urinary urgency episodes per 24 hours, average voided volume per urination, average number of daytime urinations, and average number of nocturnal urinations.

- 1) Summary statistics will be calculated for the measured values at each evaluation time point (Weeks 0, 4, 8, and 12) and the changes and percentage changes from baseline (Week 0) to Week 4, 8, and 12 of the treatment period. The same analysis will be performed by presence or absence of CIC.
- 2) Paired t-tests for the measured values at baseline (Week 0) and Weeks 4, 8, and 12 of the treatment period will be performed.
- 3) For the measured values at each evaluation time point (Weeks 0, 4, 8, and 12) and the changes and percentage changes from baseline (Week 0) to Weeks 4, 8, and 12 of the treatment period, the 95% confidence interval for the difference between the placebo group and the TAC-302 group will be calculated. The same analysis will be performed by presence or absence of CIC.
- 4) For the changes and percentage changes from baseline (Week 0) to each evaluation time point (Weeks 4, 8, and 12), student's t test, Wilcoxon rank sum test, and van Elteren test using the allocation adjustment factors as strata⁵⁾ will be performed using the placebo group as the control.
- 5) The proportion of patients with a $\leq -50\%$ change in the average number of urgency urinary incontinence episodes per 24 hours will be calculated, and Fisher's exact test will be performed to compare the between-group difference.
- 6) The same analyses as 1) to 4) will be performed for the case where missing data at Week 12 of the treatment period are imputed with LOCF.
- 7) The change and percentage change from baseline (Week 0) will be analyzed by MMRM using treatment group, evaluation time point (Weeks 4, 8, and 12 of the treatment period), and interaction between treatment group and evaluation time point as fixed effects and baseline value, sex, and age (< 65 years or ≥ 65 years) as covariates. The least squares means in each treatment group, and the difference in the least squares mean between the placebo group and the TAC-302 group and its two-sided 95% confidence interval at each evaluation time point will be estimated. Unstructured covariance structure will be assumed, and toeplitz type will be used if convergence is not achieved. If convergence is still not achieved, the first-order autoregressive, compound symmetry, and variance component will be used in this order. The Kenward-Roger method (2009) will be used to calculate degrees of freedom.

